1.4 Study Design

A total of 18 patients with unresectable locally advanced or metastatic PSqCC will be enrolled into this trial.

INCMGA00012 should be administered intravenously, at flat dose of 500 mg over one hour (\pm 15 minutes) or 30 minutes (-5/+ 15 min) using a filter on day 1 of each 28-day cycle (every 4 weeks). Infusion rate may be reduced if an infusion reaction occurs.

In the absence of progression of disease or unacceptable toxicity, treatment with INCMGA00012 will continue based on physician criteria for up to 2 years.

Tumor assessments per RECIST v.1.1 and irRECIST will be performed approximately every 8 weeks (\pm 7 days) for the first 6 months and every 12 weeks (\pm 7 days) thereafter until PD, treatment discontinuation, the start of new anti-cancer treatment, withdrawal of consent, death, or the end of study (EoS), whichever occurs first. Tumor assessments will be performed on the specified schedule regardless of treatment delays.

The primary endpoint is ORR.

For estimation of ORR, CBR, DoR, PFS, and OS, tumor response will be based on RECIST v.1.1. In patients who continue treatment beyond radiographic PD per RECIST v.1.1, tumor response (ORR, CBR, and PFS) may continue to be assessed using irRECIST criteria until study treatment discontinuation.

Safety assessments will include the incidence, nature, and severity of AEs and laboratory abnormalities graded per the NCI-CTCAE v.5.0. Laboratory safety assessments will include the regular monitoring of hematology, blood chemistry, coagulation, and thyroid function testing.

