- The duration of response (DoR) is defined as the time from start dose of first tumor response (either CR or PR) to disease progression or death due to any cause. The DoR will be calculated for the patients with unconfirmed CR or PR.
- The Time to Progression (TTP) is defined as the time from start dose to objective tumor progression or clinical disease progression (TTP does not include deaths). Patients with no progression will be censored at the date of their last evaluable imaging previous 35 days after last dose administration date.
- The Time to Response (TTR) is defined as the time from start dose to unconfirmed ORR date. Patients without ORR will be censored at the date of their last evaluable imaging previous 35 days after last dose administration date.
- Maximum Tumor Shrinkage (best percentage of change from baseline in the size of target tumor lesions) is defined as the biggest percentage of tumor shrinkage from baseline (obtained from the sum of the largest diameters of the target lesions).

5.4.1.2 irRECIST

The following results will be reported in all patients and in patients with measurable disease:

- The response assessment of the tumor is defined as best response according to:
 - irCR: complete disappearance of all measurable and non-measurable lesions. Lymph nodes must decrease to < 10 mm in short axis. Confirmation of response is not mandatory.
 - irPR: decrease of $\geq 30\%$ in Total Measured Tumor Burden (TMTB) relative to baseline, non-target lesions are irNN, and no unequivocal progression of new non-measurable lesions.
 - irSD: failure to meet criteria for irCR or irPR in the absence of irPD.
 - irNN: no target disease was identified at baseline and at follow-up the patient fails to meet criteria for irCR or irPD.
 - irPD: minimum 20% increase and minimum 5 mm absolute increase in TMTB compared to nadir, or irPD for non-target or new non-measurable lesions. Confirmation of progression is recommended minimum 4 weeks after the first irPD assessment.
 - irNE, used in exceptional cases where insufficient data exists.

- irORR is defined as the proportion of participants with irCR or irPR. Participants who do not have on-study radiographic tumor re-evaluation, who received anti-tumor treatment other than the study medication prior to reaching an irCR or irPR, or who died, progressed, or dropped out for any reason prior to reaching an irCR or irPR will be counted as non-responders in the assessment of irORR.

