5.4.4 Secondary Efficacy Analysis

Secondary efficacy results will be reported for the FAS and PP set.

For binary endpoints, the number and proportion of patients with response with the 95% Pearson-Clopper CI will be calculated.

The time to event endpoints will be performed with maximum likelihood method (MLM) for exponential distribution test, at nominal level of 0.05. Number and percentage of events will be described. The median, 6-month, 1 and 2-year

survival rates and 95% confidence intervals will be provided based on exponential MLM and Kaplan-Meier method. Swimmer plots for time-to-event endpoints will be provided.

For continuous outcome (maximum tumor shrinkage) we will use statistics of central tendency (median with 95%CI) and dispersion (range and interquartile range). We will provide waterfall plots of maximum tumor shrinkage from baseline. The duration of response has also plotted with bar plots.

For all tests, we will use two-sided P-values with alpha=0.05 level of significance. P-values emerging from these analyses will not be interpreted in a confirmative sense; they will be considered of descriptive nature only.

Table 2. Secondary Efficacy Estimands

Estimand	Population	Variable	Intercurrent event strategy	Summary measure
Secondary 1	FAS set	PFS	
 - Patients with no progression or death will be censored at the date of their last evaluable imaging previous 35 days after last dose administration date. - If no post-baseline tumor assessment is available, patients will be censored at the date of treatment initiation + 1 day. - Data for patients with an event who missed two or more scheduled assessments immediately prior to the event will be censored at the last tumor assessment prior to the missed visits. 	
Kaplan-Meier plot, number and proportion of events, median survival time, 6 months, 1- and 2-year survival rates with corresponding 95% CI.
 
Swimmer plot will be provided.

Sensitivity 1 to Secondary 1	PP set	PFS	Same as above	Same as above

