Secondary 7	FAS set	OS	
 - Patients who are not reported as having died will be analyzed as censored observations on the date they were last known to be alive. - If no post-baseline tumor assessment is available, patients will be censored at the date of treatment initiation + 1 day. 	Kaplan-Meier plot, number and proportion of events, median survival time, 1- and 2-year survival rates with corresponding 95% CI.
Sensitivity to secondary 7	PP set	OS	Same as above	Same as above
Secondary 8	FAS set	TTR	
 - Patients with no response will be censored at the date of their last evaluable imaging previous 35 days after last dose administration date. 	Kaplan-Meier plot, number and proportion of events, median survival time, 1- and 2-year survival rates with corresponding 95% CI.
Sensitivity to secondary 8	PP set	TTR	Same as above	Same as above
Secondary 9	FAS patients with overall response	DoR	
 - Patients with no progression or death will be censored at the date of their last evaluable imaging previous 35 days after last dose administration date. - If no post-response tumor assessment is available, patients will be censored at the date of treatment response + 1 day. - Data for patients with an event who missed two or more scheduled assessments immediately prior to the event will be censored at the last tumor assessment prior to the missed visits. 	Kaplan-Meier plot, number and proportion of events, median survival time, 1- and 2-year survival rates with corresponding 95% CI.
Sensitivity to secondary 9	PP patients with overall response	DoR	Same as above	Same as above
Secondary 11	FAS set	Maximum Tumor Shrinkage	Only observed cases will be used	Median, range, mean, standard deviation, and interquartile range. Waterfall plots describing the percentage of change in target tumor lesions
Sensitivity to secondary 11	PP set	Maximum Tumor Shrinkage	Same as above	Same as above

Estimand	Population	Variable	Intercurrent event strategy	Summary measure

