5.4.5 Handling of Missing Data

Study variables could be missing for patients who withdrawn from the trial or for specific visits. We will report reasons for withdrawal.

Patient with missing in response outcomes will be considered as no responders. Patients without any post-baseline assessment will be considered as non-responders or without clinical benefit.

The analysis of timed endpoints is based on a Kaplan-Meier method, therefore, not affected by patient withdrawals (as they are censored) provided that dropping out is unrelated to prognosis.

For the analysis of maximum tumor shrinkage only observed cases will be used.

The other variables will be managed with simple imputations methods (last observation carried forward). The effect that any missing data might have on results will be assessed via sensitivity analysis.

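### Kaplan-Meier time to response censors patients who progressed or died without responding, so the curve can overstate the probability of response

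*SAP*

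**What the plan says.** SAP 5.4.1.1 gives the definition: "The Time to Response (TTR) is defined as the time from start dose to unconfirmed ORR date". The censoring rule follows: "Patients without ORR will be censored at the date of their last evaluable imaging previous 35 days after last dose administration date". Table 2 in SAP 5.4.4 (Secondary 8) repeats it for the full analysis set (FAS): "Patients with no response will be censored at the date of their last evaluable imaging previous 35 days after last dose administration date". The summary measure in that row is: "Kaplan-Meier plot, number and proportion of events, median survival time, 1- and 2-year survival rates with corresponding 95% CI".

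The text of SAP 5.4.4 adds an exponential model for time-to-event endpoints in general: "survival rates and 95% confidence intervals will be provided based on exponential MLM and Kaplan-Meier method". Table 3 in SAP 5.4.6 carries TTR into the subgroup analyses, with adjusted hazard ratios, medians and 6-month rates.

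Three other places bear on the point:

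- SAP 5.4.5 says Kaplan-Meier analyses are not affected by withdrawals, but only "provided that dropping out is unrelated to prognosis".
- SAP 1.4 says that, in patients treated beyond RECIST v.1.1 progression, response may continue to be assessed by irRECIST.
- SAP 5.4.1.2 counts patients who died or progressed before an immune-related response as non-responders for irORR.

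Neither document names a cumulative incidence or competing-risk method. TTR is not a protocol endpoint. SAP 5.7 records that it was added and that time to progression was dropped, so the SAP holds its only specification.

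**The concern.** Kaplan-Meier assumes that a censored patient remains able to have the event, at the same rate as those still under observation. That is reasonable for a patient still on treatment and unprogressed at data cut-off. It cannot be true of a patient who has died. It is not true either of one who progressed first, if response after progression belongs to irRECIST. Censoring these patients hands their share of the probability to later responders. The SAP's own condition, that dropping out be unrelated to prognosis, fails for exactly these exits.

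At stake is how a descriptive result is read. TTR and ORR use the same event, the first unconfirmed response, in the same 18 patients. The report could show one response probability from the proportion and a higher one from the curve. A median TTR read off the curve could be taken to mean that half the patients responded when they did not.

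**Working it through.** **Plan's own figure.** The documents state no expected value for TTR. The one design figure, at least 3 responders among 16, does reproduce: P(X ≥ 3 | 16, 0.05) = 0.043 and P(X ≥ 3 | 16, 0.25) = 0.803. It does not depend on TTR.

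**Inputs from the documents.** N = 18 and a target ORR of 25% (SAP 1.6). Scans are every 8 weeks for 6 months, then every 12 weeks (SAP 1.4), taken here as weeks 8, 16, 24, 36 and 48. The censoring rule is that of SAP 5.4.1.1.

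**Assumed inputs.** When responses occur, and how fast non-responders progress or die.

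**Formulas.** Kaplan-Meier: S = product over response times of (1 − d/n), where d is the number responding and n the number still at risk. The curve's estimate of the probability of response is 1 − S. If every non-responder is followed to progression, death or the end of scanning, the cumulative incidence of response is simply responders/18.

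**Example 1: no excess.** Three responders, all at week 8, nobody censored earlier: 1 − 15/18 = 16.7%, equal to 3/18.

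**Example 2.** Four responders, at weeks 8, 8, 16 and 24. Fourteen non-responders progress or die and are last scanned at week 8 (7), week 16 (4) and week 24 (3).

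| Week | At risk | Responses | Factor |
|---|---|---|---|
| 8 | 18 | 2 | 16/18 |
| 16 | 18 − 2 − 7 = 9 | 1 | 8/9 |
| 24 | 9 − 1 − 4 = 4 | 1 | 3/4 |

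S = 16/18 × 8/9 × 3/4 = 0.593, so 1 − S = 40.7%. The observed proportion is 4/18 = 22.2%.

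**Example 3: a median is reached.** Five responders: three at week 8, one at week 16, one at week 36. One non-responder has no scan (assumed censored at the start); the others leave at week 8 (7), week 16 (2), week 24 (1) and week 48 (2). S = 14/17 × 6/7 × 2/3 = 0.471, so 1 − S = 52.9% against 5/18 = 27.8%. A median TTR would be reported although 13 of 18 never respond.

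**Exponential model on Example 2.** Time at risk is 8 + 8 + 16 + 24 = 56 weeks in responders and 7×8 + 4×16 + 3×24 = 192 weeks in non-responders, 248 in all. The rate is 4/248 = 0.0161 per week. The fitted median is ln 2/0.0161 = 43 weeks, and the fitted probability of response by 52 weeks is 1 − exp(−52 × 4/248) = 57%. This model returns a finite median as soon as one patient responds.

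**Simulation.** True ORR 25%, N = 18. Non-responders' time to progression is exponential, with progression recorded at the next scan. The last column counts only trials in which the curve reaches 50% while fewer than half respond.

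| Non-responder median time to progression | Response timing | Mean 1 − S | Median TTR reached, fewer than half responding |
|---|---|---|---|
| 12 weeks | all at week 8 | 25% | 0% |
| 12 weeks | 60/25/15% at weeks 8/16/24 | 33% | 10% |
| 12 weeks | even over weeks 8, 16, 24 | 38% | 20% |
| 8 to 24 weeks | full range from all at week 8 to even | 25% to 46% | 0% to about 39% |

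The excess grows with later responses and earlier progression. It vanishes only when no non-responder is censored before a later response. In practice that means all responses at the first scan, with nobody censored earlier.

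**The case against.** Four objections deserve weight.

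1. **The excess is not inevitable.** If responses come at the first scan, as Example 1 shows, curve and proportion agree. This stands. A reader might infer that the curve will overstate response in this trial, or by a particular amount. The documents do not support that, because they give neither response timing nor progression rates.

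2. **The correct proportion is still reported.** The same Table 2 row asks for the number and proportion of events, and ORR is a FAS proportion with missing outcomes counted as non-response (SAP 5.4.2). This stands too. A reader might infer that the flaw reaches the primary result or the decision on the study. It does not: both rest on the exact binomial test of ORR. TTR carries no decision rule, and the SAP calls secondary p-values descriptive.

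3. **Not every non-responder has a competing event.** A patient still on study at cut-off, or off treatment for toxicity without progression, may properly be censored. This stands, and the remedy must keep ordinary censoring for patients still at risk of response. The examples assume that those who left early had progressed or died.

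4. **The SAP does not say outright that response after progression is excluded.** Best response is taken across all time points to 35 days after the last dose, with no stated cut at first progression. For progressors the argument therefore rests on SAP 1.4 and its move to irRECIST, which is the natural reading but an inference. For deaths no inference is needed.

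None of this rescues the rule. An unqualified Kaplan-Meier analysis remains the wrong estimator when progression and death remove patients from the chance of response.

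**Conclusion.** The point holds in conditional form. As specified, the TTR curve is never below the observed response proportion, and it lies above it whenever a non-responder is censored before a later response. The cause is that progression and death without response are handled as ordinary censoring.

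Under the stated assumptions the average endpoint of the curve runs from no excess (25%) to 46% for a true ORR of 25%. A misleading median appears in anything from no trials to about 39% of them. These ranges reflect assumed timings and are not forecasts for this trial.

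The consequence is limited to the TTR curve, the medians and rates taken from it (Kaplan-Meier and exponential), and the TTR subgroup row. It is worth correcting before analysis, because the SAP is the only specification of TTR and the correction is cheap.

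**What to change.** In SAP 5.4.1.1 and Table 2 (Secondary 8), replace the Kaplan-Meier analysis of TTR by one of two options:

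- **Preferred for simplicity:** describe TTR in responders only, with median and range.
- **If a curve over all FAS patients is wanted:** estimate the cumulative incidence of response, with progression or death without response as competing events. Apply ordinary censoring only to patients still at risk of response when last assessed.

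Under either option, delete the Kaplan-Meier and exponential median and the 1- and 2-year TTR rates. Bring the TTR row of Table 3 into line. State whether a response after first RECIST v.1.1 progression counts, in the same terms for TTR and ORR.

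The cost is SAP wording and one changed output, with the subgroup row aligned. Progression and death dates are already needed for PFS and OS, so no new data are required. The responder-only summary says nothing about how many patients respond; ORR already covers that.

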4.2 Inclusion Criteria

Patients must meet ALL the following inclusion criteria to be enrolled in the study:

1. Patients have been informed about the nature of study, and have agreed to participate in the study, and signed the informed consent form (ICF) prior to participation in any study-related activities.
2. Male patients \geq 18 years of age at the time of signing ICF.
3. Eastern Cooperative Oncology Group (ECOG) Performance Status (PS) 0-1.
4. Life expectancy \geq 12 weeks.
5. Histologically-proven PSqCC.

6. Locally advanced unresectable or metastatic stage 4 PSqCC that is not amenable to resection with curative intent (T4 or N3 or M1).
7. Radiological evidence of locally advanced or metastatic disease.
8. Patients must have measurable disease or evaluable disease according to Response Evaluation Criteria in Solid Tumors (RECIST) version (v.)1.1 criteria.
9. Patients must agree to provide a tumor tissue sample from a metastatic site or the primary tumor at the time of study entry, with the exception of patients for whom tumor biopsies cannot be obtained (e.g., inaccessible tumor or subject safety concern) that may submit an archived tumor specimen only upon agreement from the Sponsor. If feasible, patients will also be given the option of providing a tumor tissue sample at disease progression from metastasis or primary tumor (if tumor biopsies cannot be obtained for inaccessible lesion or subject safety concern).
10. Willingness and ability to provide blood samples (liquid biopsy) at the time of inclusion, after 2 cycles of study treatment (C3D1), and upon PD or study termination.
11. Adequate organ function:
 - Hematological: White blood cell (WBC) count $> 3.0 \times 10^9/L$, absolute neutrophil count (ANC) $\geq 1.5 \times 10^9/L$, platelet count $\geq 75.0 \times 10^9/L$, and hemoglobin > 9.0 g/dL.
 - Hepatic: Bilirubin ≤ 1.5 times the upper limit of normal (\times ULN) ($< 3 \times$ ULN in the case of Gilbert's disease); aspartate transaminase (AST), and alanine transaminase (ALT) ≤ 2.5 times \times ULN (in the case of liver metastases $\leq 5 \times$ ULN); Albumin > 2.5 mg/mL.
 - Renal: Serum creatinine $\leq 1.5 \times$ ULN; alternately measured or calculated creatinine clearance ≥ 30 mL/min with creatinine levels $> 1.5 \times$ institutional ULN (glomerular filtration rate [GFR] can also be used in place of creatinine or creatinine clearance).

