3.4 Exploratory Endpoints

- ORR, CBR, and 6-month PFS as per irRECIST.
- Relationship between tumor- and/or immune-related biomarkers, and efficacy in tumor tissue and/or liquid biopsy.

- Changes from baseline in the CD4-positive cell count and HIV viral load in participants who are known to be HIV-positive.

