5.4.1 Response Efficacy Definitions

5.4.1.1 RECIST V.1.1

Overall response according RECIST v1.1 will be obtained from target lesion response, non-target lesion response and new lesions, as follows:

Target Lesions	Non-target Lesions	New Lesions	Overall Response
CR	CR	No	CR
CR	Non-CR/non-PD	No	PR
CR	Not all evaluated	No	PR
PR	Non-CR/Non-PD or not all evaluated	No	PR
SD	Non-CR/Non-PD or not all evaluated	No	SD
Not all evaluated	Non-PD	No	NE
PD	Any	Yes or No	PD
Any	PD	Yes or No	PD
Any	Any	Yes	PD

The following results will be reported in all patients and in patients with measurable disease.

- The unconfirmed Best Overall Response, defined as the best overall response recorded from the start of the study treatment until 35 days after last dose administration date and confirmation of response is not required.
 - o When CR or PR is the best response across all time points, then best overall response will be CR or PR respectively.
 - o When SD is the best response for ≥ 12 weeks the best overall response will be SD ≥ 12 w.
 - o When SD is the best response for < 12 weeks the best overall response will be SD < 12 w.
 - o When non-target disease only and Non-CR/Non-PD is the best response for ≥ 12 weeks the best overall response will be SD ≥ 12 w.
 - o When non-target disease only and Non-CR/Non-PD is the best response for < 12 weeks the best overall response will be SD < 12 w.
 - o When PD is the best response across all time points, best overall response will be PD.
 - o When there is no evaluable tumor assessments best overall response will be NE.
- The confirmed Best Overall Response, defined as the best overall response recorded from the start of the study treatment until 35 days after last dose administration date and confirmation of response is required.
 - o When CR or PR is the best response for ≥ 4 weeks then best overall response will be CR or PR respectively.
 - o When SD is the best response for ≥ 12 weeks the best overall response will be SD ≥ 12 w.
 - o When SD is the best response for < 12 weeks the best overall response will be SD < 12 w.
 - o When non-target disease only and Non-CR/Non-PD is the best response for ≥ 12 weeks the best overall response will be SD ≥ 12 w.
 - o When non-target disease only and Non-CR/Non-PD is the best response for < 12 weeks the best overall response will be SD < 12 w.
 - o When PD is the best response across all time points, best overall response will be PD.

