- irCBR is defined as the proportion of participants with irCR or irPR or irSD. Participants who do not have on-study radiographic tumor re-evaluation, who received anti-tumor treatment other than the study medication prior to reaching an irCR or irPR or irSD, or who died, progressed, or dropped out for any reason prior to reaching an irCR or irPR or irSD will be counted as non-responders in the assessment of irCBR.
- irPFS: is defined as the period from the date of treatment initiation to the date of the first documentation of objective progression of disease (irPD) or death due to any cause in absence of documented irPD. Confirmation of progression is recommended minimum 4 weeks after the first irPD assessment. Participants lacking an evaluation of tumor response after treatment initiation will have their PFS time censored on the date of treatment initiation with the duration of a day. Participants with documentation of irPD or death after a long interval (2 or more incomplete or non-evaluable assessments) since the last tumor assessment will be censored at the time of last objective assessment that did not show PD. The length of irPFS will be calculated as irPFS time (months) = [(progression, death date or censor date) – treatment initiation date +1]/30.4.
- 6-months PFS rate is defined as the proportion of patients who are alive and progression-free at 6 months from the date of first dose of study treatment based on irRECIST criteria.

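### SAP 5.4.1.2 uses irNN both as a lesion status and as a patient category, so the irPR rule misclassifies some responders as irSD on either reading

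*SAP*

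**What the plan says.** SAP 5.4.1.2 (irRECIST) lists the response categories.

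- **irPR** needs a TMTB decrease of at least 30% "relative to baseline, non-target lesions are irNN, and no unequivocal progression of new non-measurable lesions".
- **irNN** is defined two bullets later: "irNN: no target disease was identified at baseline and at follow-up the patient fails to meet criteria for irCR or irPD". Neither document defines it anywhere else. Protocol 6.4.4 deals with confirming progression and treating beyond it, and defines neither irPR nor irNN.
- **irSD** is the default category: "irSD: failure to meet criteria for irCR or irPR in the absence of irPD".

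The rates follow from these categories: "irORR is defined as the proportion of participants with irCR or irPR" and "irCBR is defined as the proportion of participants with irCR or irPR or irSD". The irCBR definition sets no minimum duration for irSD and does not list irNN.

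For RECIST v.1.1, the overall-response table in SAP 5.4.1.1 has one row for target PR, and its non-target entry is "Non-CR/Non-PD or not all evaluated".

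Patients without target lesions can enter the trial. Inclusion criterion 8 in Protocol 4.2 reads: "Patients must have measurable disease or evaluable disease according to Response Evaluation Criteria in Solid Tumors (RECIST) version (v.)1.1 criteria".

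SAP 3.4 lists the irRECIST results as exploratory: "ORR, CBR, and 6-month PFS as per irRECIST". SAP Table 2 nevertheless carries irORR as an estimand labelled Secondary 13, and Table 4 gives it a subgroup analysis. Protocol 8.4.3 and SAP 5.4.7 plan a comparison of RECIST with irRECIST.

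**The concern.** One label does two jobs. Inside the irPR bullet, irNN describes non-target lesions. In its own bullet it describes a patient who had no target disease at baseline. A patient of that second kind has no baseline target measurement from which a 30% fall could be calculated. The condition as defined therefore cannot hold together with the shrinkage that irPR requires.

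Anyone who fails irPR without irCR or irPD drops to irSD, and irSD does not count in irORR. Protocol 6.4.4 gives the reason for using irRECIST: standard RECIST may not describe responses to immunotherapy precisely. A rule that turns RECIST partial responders into irRECIST non-responders works against that reason. The comparison of the two criteria would then partly measure a drafting difference. A programmer has to guess the meaning, and the guess changes the result.

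**Working it through.** The plan states no figure to reproduce here, so the check is on the definitions.

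**Step 1. The patients concerned.** Take a patient with target disease at baseline, a TMTB fall of at least 30%, no irPD from any source, and not irCR. His non-target lesions, if evaluated, follow one of three patterns: none present, all disappeared, or persisting without progression.

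**Step 2. Apply each reading of the irPR rule.**

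| Non-target lesions | irNN as the SAP defines it | irNN read as lesion-level non-CR/non-PD | Rule requiring only that non-target lesions are not irPD |
|---|---|---|---|
| None present | Unclear: irPR only if the condition lapses when it has nothing to apply to | irPR on the same proviso | irPR |
| All disappeared | irSD | irSD | irPR |
| Persisting, no progression | irSD | irPR | irPR |
| Patterns reaching irPR | 0 of 3, or 1 of 3 if the condition lapses | 2 of 3 if the condition lapses, otherwise 1 of 3 | 3 of 3 |

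No reading of the current text gives irPR in all three patterns. On the lesion-level reading, the better non-target outcome (disappearance) gives the worse category.

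**Step 3. Compare with RECIST in SAP 5.4.1.1.** The target-PR row gives overall PR when non-target lesions persist without progression. Under the literal irRECIST text the same patient is irSD. The RECIST row also accepts non-target lesions that were not all evaluated, on which the irPR bullet is silent. However, the RECIST row has no entry for non-target CR or for no non-target lesions, so it shares part of the gap.

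**Step 4. Size per patient.** The planned full analysis set is 18 (SAP 1.6). One responder moved from irPR to irSD changes irORR by 1/18 = 0.056, or 5.6 percentage points.

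**Step 5. What does not change.**

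- Primary ORR uses unconfirmed RECIST v.1.1 CR or PR (SAP 5.4.1.1 and Table 1). Neither irPR nor irNN enters.
- irPFS depends on irPD and death only.
- irCBR is the same for these patients, because irSD counts in it.

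**Step 6. A side effect of the double use.** A patient without target disease who has neither irCR nor irPD meets the irNN definition. He also meets the irSD definition, since he fails irCR and irPR without irPD. irCBR counts irSD and does not mention irNN, so the SAP does not settle whether he has clinical benefit. For RECIST it does: SAP 5.4.1.1 assigns non-target-only, Non-CR/Non-PD patients to SD by duration.

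**The case against.** The strongest answer is that the literal reading is not what the authors meant. The irPR bullet applies irNN to lesions, the irPD bullet in the same list also applies its label to lesions, and the RECIST table has the lesion-level Non-CR/Non-PD in the matching place. On that reading irPR is attainable for patients with persisting non-target lesions. This stands as the likely intention, but the SAP does not state it, and it still fails the patient whose non-target lesions have all disappeared.

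A second answer is that the RECIST table has the same hole. It would be unfair to read irRECIST to the letter and RECIST sensibly, then report the difference as a finding. Protocol 6.4.2 defines PR by target lesions alone, which supports a sensible reading on the RECIST side. The point is fair, and the remedy is to correct both.

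A third is that the stakes are modest: irORR is exploratory and SAP 5.4.3 treats p-values from such analyses as descriptive. That also stands.

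A reader might go further and infer that no patient can ever be irPR, so that irORR reduces to irCR alone. The documents do not support this. For a patient with target lesions only, the non-target condition has nothing to apply to and may simply lapse. A reader might also set an irORR of 0% against a RECIST ORR of 25%, about 0.25 × 18 = 4.5 responders. That contrast needs the literal reading, every response partial, and target-only patients failing too. The 25% is the RECIST design alternative in SAP 1.6, not an irRECIST rate.

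**Conclusion.** The point holds as a defect in the irPR definition. On the literal text, patients with both target and non-target lesions and a TMTB fall of at least 30%, without irCR or irPD, are irSD and non-responders in irORR. For patients with no non-target lesions the text is unclear. On the lesion-level reading the loss narrows to patients whose non-target lesions have all disappeared, but it does not vanish.

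The effect is 5.6 percentage points of irORR per misclassified patient, assuming the planned 18 in the full analysis set. It carries into the irORR subgroup analysis and the comparison of RECIST with irRECIST. The total effect cannot be estimated, because the documents give no irRECIST response rates and no split of patients by lesion type. The primary analysis and its decision rule are untouched. The wording should be corrected before irRECIST responses are derived.

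**What to change.** In SAP 5.4.1.2:

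1. Define irPR as a TMTB decrease of at least 30% from baseline, with non-target lesions not irPD (absent, irCR, non-irCR/non-irPD, or not all evaluated) and no unequivocal progression of new non-measurable lesions.
2. Give the lesion-level status its own label, such as non-irCR/non-irPD.
3. Keep irNN as the category for patients without target disease at baseline, and exclude those patients from irSD.
4. State how irNN counts in irCBR.

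In SAP 5.4.1.1, extend the target-PR row of the RECIST table to cover non-target CR and no non-target lesions, so that the two criteria are compared on the same basis.

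The cost is a few sentences in the SAP, one table row and a small change to the derivation code. No new data are needed and the primary analysis does not change.
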